3.2 DRUG ADMINISTRATION

General Rule

For participants enrolled on the phase I portion of the protocol a window of +/- 14 days for a scheduled treatment is allowed in the event of scheduling issues (i.e., holiday, bad weather or other scheduling issues). For participants enrolled on the phase II portion of the protocol a window of +/- 7 days for a scheduled treatment is allowed in the event of scheduling issues (i.e., holiday, bad weather or other scheduling issues). The minimum time between administrations of a similar agent is 11 days. Where feasible PRGN-2009 should be administered first, followed by M7824 (when given).

3.2.1 PRGN-2009

On the phase I portion of the protocol PRGN-2009 will be administered on D1, D15, D29 followed by booster vaccines every 4 weeks for up to a year. The dose level given as booster will be the same dose participants will be receiving for D1, D15 and D29. On the phase II portion of the protocol PRGN-2009 will be administered on just D1 and D15.

3.2.1.1 Refer to Sections 14.1.4 Pharmacy Preparation and 14.1.5 Vaccine Preparation

3.2.1.2 Administration Procedures

- Injection Volume – The injection volume for both doses is 1.0 ml.

- Injection Route – The route of injection is by subcutaneous injection using a 1.0 ml syringe.

Follow your standard institutional clinical procedures for preparation of the subject's injection site, subcutaneous injection and post-injection bandaging of the injection site. PRGN-2009 is a non-replicating, non-integrating adenoviral vector. Since the parental adenovirus is classified as biosafety level 2 (BSL2), PRGN-2009 should be handled as BSL2 material for disposal of all materials that were used in the dose administration. Spills of PRGN-2009 should be decontaminated using a solution of 10% bleach.

3.2.2 M7824

Subjects enrolled to Arm 1B will receive M7824 via IV infusion over 1 hour (-10 minutes / +20 minutes, that is, over 50 to 80 minutes) once every 2 weeks for up to a year (Arm 1B). M7824 will be administered as a "flat" dose of 1,200 mg independent of body weight. M7824 is administered as an intravenous infusion with a mandatory 0.2 micron in-line filter. Infusion of M7824 can be administered through a PIV or CVAD or port with titanium as the main material.

Current experience revealed that IRRs to M7824 occur seldomly and are generally mild to moderate in severity. Therefore, administration of a premedication is generally not required.

In order to mitigate potential infusion-related reactions, premedication with an antihistamine and with acetaminophen (for example, 25-50 mg diphenhydramine and 500-650 mg acetaminophen) within approximately 30 to 60 minutes prior to dosing of M7824 is optional and at the discretion of the Investigator.

Management of symptoms should follow the guidelines shown in **Table 2**.

3.2.2.1 Immediate Hypersensitivity Reaction

Hypersensitivity reactions may require immediate intensive care. M7824 should be administered in a setting that allows for immediate access to an intensive care unit or equivalent environment and administration of therapy for anaphylaxis, such as the ability to implement immediate resuscitation measures. Steroids (dexamethasone 10 mg), epinephrine (1:1,000 dilution), allergy medications (IV antihistamines), bronchodilators, or equivalents, and oxygen should be available for immediate access.

A complete guideline for the emergency treatment of anaphylactic reactions according to the Working Group of the Resuscitation Council United Kingdom and can be found at <https://www.resus.org.uk/pages/reaction.pdf>.

3.2.2.2 Flu-Like Symptoms

Treatment is based on clinical assessment and at the discretion of the Investigator. For prophylaxis of flu like symptoms, a nonsteroidal anti-inflammatory drug (NSAID), e.g., ibuprofen 400 mg or comparable NSAID dose, may be administered 2 hours before and 8 hours after the start of each IV infusion.

3.3 DOSE MODIFICATIONS

3.3.1 Discontinuation

Phase 1 and Phase 2:

Treatment with individual agents (PRGN-2009 alone or in combination with M7824) will be discontinued in participants experiencing specific adverse events; subjects will however still remain on study for follow up of survival. Treatment discontinuation will occur in any participant experiencing a DLT-defining toxicity and in the case of:

- Any Grade 4 or higher adverse drug reactions (ADRs) as defined by CTCAE v5.0 and assessed as possibly related to that agent by the Investigator, **except** for any of the following:
 - Laboratory values that are asymptomatic or resolve to Grade ≤ 1 or baseline grade within 7 days without medical intervention.
 - Any endocrinopathy that can be medically managed with hormone replacement.
- Any Grade 3 ADRs possibly attributed to that agent **except** for any of the following:
 - Grade 3 flu-like symptoms or fever, as well as associated symptoms of fatigue, headaches, nausea, emesis which can be controlled with conservative medical management.
 - Tumor flare phenomenon defined as local pain, irritation, or rash localized at sites of known or suspected tumor.
 - Grade 3 Hgb decrease (< 8.0 g/dL) that is clinically manageable with blood transfusions or erythroid growth factor use.
 - Grade 3 laboratory values that are asymptomatic or resolve to Grade ≤ 1 or baseline grade within 7 days with medical management.
 - Keratoacanthoma and squamous cell carcinoma of the skin.
 - Any endocrinopathy that can be medically managed with hormone replacement.
 - Any other grade 3 adverse drug reaction that resolves to grade ≤ 1 or baseline grade within 72 hours.

3.3.2 Dose Delay

Individual agents should be withheld for any Grade 2 or 3 ADR possibly attributed to that agent until resolution to Grade ≤ 1 unless the ADR in the opinion of the investigator is not clinically relevant or can be medically managed with minimal risk to the participant. Should a clinically relevant grade 2 or 3 ADR persist for more than 4 weeks, consideration should be given to discontinuing treatment with that individual agent at the discretion of the investigator.

For non-medical logistical reasons, unrelated acute illnesses, or palliative radiation, scheduled assessments and dosing can be delayed up to 2 months. Where at all possible, dosing should be restarted to keep in line with the original treatment schedule.

3.3.3 Study Accrual Halting Rules

Accrual will be halted if:

- Phase 1 and Phase 2:
 - There is an occurrence of any death (other than death related to progressive disease or accidental death) that occurs within 30 days of administration of study agents (PRGN-2009 and M7824) for both Phase 1 and Phase 2.
- Phase 2 only:
 - There is a delay in initiation of definitive standard of care therapy of 4 weeks or more beyond the planned start date due to treatment-related toxicities from HPV vaccine in two participants.

- There is occurrence of treatment-related ADRs from HPV vaccine of either Grade 4 (except for laboratory values that are asymptomatic or resolve to Grade ≤ 1 or baseline within 7 days) or of Grade 3 not resolving to Grade ≤ 1 or baseline within 7 days in two participants.

The IRB and the sponsor will be notified if one of the study accrual halting rules has been reached.

The accrual halt will be lifted once the data has been reviewed and there has been a reassessment of available safety information prior to reopening the study to accrual and allowing the study to proceed.

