6 DATA COLLECTION AND EVALUATION

6.1 DATA COLLECTION

The PI will be responsible for overseeing entry of data into a 21 CFR Part 11-compliant data capture system provided by the NCI CCR and ensuring data accuracy, consistency and timeliness. The principal investigator, associate investigators/research nurses and/or a contracted data manager will assist with the data management efforts. Primary and final analyzed data will have identifiers so that research data can be attributed to an individual human subject participant.

All adverse events, including clinically significant abnormal findings on laboratory evaluations, regardless of severity, will be followed until return to baseline or stabilization of event. Document AEs from the first study treatment, study day 1, through 28 days after the subject received the last product administration. After 28 days, only adverse events which are serious and related to the study investigational agent need to be recorded. For participants enrolled on the phase II portion of the protocol adverse events which occur while participant is being treated with standard chemoradiation and which are not attributed to immunotherapy need not be captured.

An abnormal laboratory value will be recorded in the database as an AE **only** if the laboratory abnormality is characterized by any of the following:

- Results in discontinuation from the study;
- Is associated with clinical signs or symptoms;
- Requires treatment or any other therapeutic intervention;
- Is associated with death or another serious adverse event, including hospitalization;
- Is judged by the Investigator to be of significant clinical impact; and/or
- If any abnormal laboratory result is considered clinically significant, the investigator will provide details about the action taken with respect to the test drug and about the participant's outcome.

End of study procedures: Data will be stored according to HHS, FDA regulations, and NIH Intramural Records Retention Schedule as applicable.

Loss or destruction of data: Should we become aware that a major breach in our plan to protect subject confidentiality and trial data has occurred, this will be reported expeditiously per requirements in Section [7.2.1](#).

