10.2 SAMPLE SIZE DETERMINATION

The phase I portion of the trial will be conducted using 3+3 dose escalation design evaluating the safety of PRGN-2009 at two dose levels as monotherapy and at the RP2D of PRGN-2009 in combination with a fixed dose of M7824. Using this design up to 22 participants may be enrolled on the phase I portion of the study.

In arm 2A, phase II, 20 participants with p16+ oropharyngeal cancer will be enrolled based on the following reasoning. Assume that a success for any individual participant will be defined as that participant experiencing a two-fold increase in CD3+ tumor infiltrating T cells post treatment compared with pre-treatment. With 20 participants, there would be 80.4% power to detect a difference between 50% and 80% of participants experiencing a success in arm 2A, with an exact binomial test using a one-sided 0.05 significance level. As an illustration, with 20 participants, if 15 participants were able to have a two-fold increase, the lower two-sided 90% confidence bound on 15/20 is 54.4% and the upper two-sided 90% confidence bound is 89.6%. Thus, 15/20 participants would demonstrate the intended magnitude of effect. If 14/20 had this outcome, the lower 90% two-sided bound is 49.2% and the upper two-sided 90% bound is 86.0%, essentially demonstrating nearly the same result.

Expecting that up to 22 evaluable participants will enroll on the phase I portion of the study, that 20 evaluable p16+ oropharyngeal cancer participants will enroll on phase II 2A, and that up to 2 evaluable HPV-SNSCC participants may enroll on phase II 2A, a total of up to 44 evaluable participants will be planned to enroll on this protocol. To allow for a few inevaluable participants the accrual ceiling for this protocol will be set at 50 participants.

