14.1.2 Toxicity

PRGN-2009 has not been tested in humans. PRGN-2009 antigen was successfully evaluated in three different types of *in vitro* analyses designed to identify potential oncogenicity of novel DNA in mammalian cells. The HPV PRGN-2009 antigen did not induce an oncogenic profile in the host cells in any assay, whereas cells transformed with wild type HPV oncogene versions unambiguously displayed morphological and phenotypic changes consistent with oncogenesis, both qualitatively and quantitatively. This data provides confidence that the HPV PRGN-2009

Abbreviated Title: Combo Immunotx in HPV OPSCC

Version Date: 09.20.2023

molecular vaccine candidate is safe for use in mammalian cells and will not induce aberrant growth consistent with carcinogenesis.

PRGN-2009 is a non-replicating, non-integrating adenoviral vector. Since the parental adenovirus is classified as biosafety level 2 (BSL2), PRGN-2009 should be handled as BSL2 material for disposal of all materials that were used in the dose preparation. Avoid generation of aerosols. Spills of PRGN-2009 should be decontaminated using a solution of 10% bleach.

This is a first in human study with PRGN-2009. Possible side effects may include injection side reaction, fever, flu like symptoms (e.g., fatigue, headache, muscle aches), poor appetite, increase in blood sugar, and skin rash.

Table 8: Summary of Treatment-Emergent Adverse Events in Phase 1/2 Study in Patients with HPV+ Malignancies (NCT04432597) (Reference: Table 7 in PRGN-2009 IB Version 3)

	Phase 1						Phase 2	
	PRGN-2009, 1 x 10 ¹¹ PU (n=3)		PRGN-2009, 5 x 10 ¹¹ PU (n=3)		PRGN-2009, 5 x 10 ¹¹ PU + M7824, 1200 mg (n=11)		PRGN-2009, 5 x 10 ¹¹ PU (n=22)	
	# of events	# of patients	# of events	# of patients	# of events	# of patients	# of events	# of patients
All TEAEs	79	3/3 (100%)	20	3/3 (100%)	132	11/11 (100%)	88	22/22 (100%)
Grade 1	46	3/3 (100%)	11	3/3 (100%)	90	10/11 (90.9%)	60	20/22 (90.9%)
Grade 2	22	3/3 (100%)	9	3/3 (100%)	35	8/11 (72.7%)	26	15/22 (68.2%)
Grade 3	11	2/3 (66.7%)	0	0	4	3/11 (27.3%)	2	2/22 (9.1%)
Grade 4	0	0	0	0	2	2/11 (18.2%)	0	0
Grade 5	0	0	0	0	1	1/11 (9.1%)	0	0
PRGN-2009 treatment-related TEAE	32	3/3 (100%)	4	2/3 (66.7%)	45	10/11 (90.9%)	53	20/22 (90.9%)
PRGN-2009 treatment-related AE \geqGrade 3	0	0	0	0	0	0	0	0
All SAEs	7	2/3 (66.7%)	1	1/3 (33.3%)	6	3/11 (27.3%)	0	0
Treatment related SAEs	0	0	0	0	0	0	0	0
DLT	0	0	0	0	0	0	0	0

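### In the Phase II accrual-halting rule, a persistent asymptomatic laboratory reaction to the vaccine counts at Grade 3 but is exempt at Grade 4

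*Combined protocol and SAP*

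**What the plan says.** Section 3.3.3 (Study Accrual Halting Rules) gives two halting triggers for Phase II only, each requiring two participants. One is a toxicity-related "delay in initiation of definitive standard of care therapy of 4 weeks or more beyond the planned start date". The other, at issue here, is vaccine-related adverse drug reactions (ADRs), with two legs:

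- **Grade 4 leg:** any such reaction, with an exemption in parentheses that closes just before the Grade 3 leg begins: "except for laboratory values that are asymptomatic or resolve to Grade ≤ 1 or baseline within 7 days) or of Grade 3 not resolving".
- **Grade 3 leg:** any reaction that has not returned to Grade 1 or lower, or to baseline, within 7 days. No laboratory or asymptomatic exemption is attached.

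The individual discontinuation rule in section 3.3.1 covers both phases and is built differently. Its Grade 4 bullet exempts "Laboratory values that are asymptomatic or resolve to Grade ≤ 1 or baseline grade within 7 days without medical intervention", and its Grade 3 bullet exempts "Grade 3 laboratory values that are asymptomatic or resolve to Grade ≤ 1 or baseline grade within 7 days with medical management". The two differ on medical management, but both exempt a laboratory value without symptoms. The dose-limiting toxicity (DLT) definition in section 3.1.1 does the same at both grades.

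Section 6.1 says when a laboratory abnormality is recorded as an adverse event. Symptoms are one route. Needing treatment is another, and so is that it "Is judged by the Investigator to be of significant clinical impact".

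**The concern.** A halting rule should be at least as sensitive to a worse event as to a milder one. Here, for one class of event, it is less sensitive. A vaccine-related laboratory ADR without symptoms that outlasts 7 days adds to the halt count at Grade 3 and adds nothing at Grade 4.

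The class is not empty by definition, because section 6.1 allows a symptom-free laboratory value to be recorded as an adverse event. Nor do the neighbouring rules catch it. At Grade 4 the same event is exempt from discontinuation under section 3.3.1, and the dose-delay rule in section 3.3.2 names only Grades 2 and 3.

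Phase II participants are newly diagnosed and receive the vaccine before definitive, potentially curative treatment, so the tolerance for an unnoticed safety signal is low.

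**Working it through.** The plan attaches no figure to this rule, so there is none to reproduce. The check is a truth table, followed by a rough estimate of how often the gap could matter.

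**1. The rule as written (section 3.3.3)**

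- Grade 4 counts unless the event is laboratory AND (asymptomatic OR resolved within 7 days).
- Grade 3 counts unless the event resolved within 7 days.

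| Type | Symptoms | Resolved within 7 days | Grade 3 | Grade 4 now | Grade 4 after fix |
|---|---|---|---|---|---|
| Laboratory | No | Yes | no | no | no |
| **Laboratory** | **No** | **No** | **counts** | **no** | **counts** |
| Laboratory | Yes | Yes | no | no | no |
| Laboratory | Yes | No | counts | counts | counts |
| Other | No | Yes | no | counts | counts |
| Other | No | No | counts | counts | counts |
| Other | Yes | Yes | no | counts | counts |
| Other | Yes | No | counts | counts | counts |

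Grade 3 counts in 4 of 8 types and Grade 4 in 5 of 8. Exactly one type is inverted. After the fix Grade 4 counts in 6 of 8, one cell has changed, and no inversion remains.

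**2. Comparison with the other rules**

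For the inverted type, sections 3.1.1 and 3.3.1 exempt both grades. Only section 3.3.3 separates them, and nothing elsewhere overrides it.

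**3. How often it could matter**

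- Treated so far (Table 8, section 14.1.2): 3 + 3 + 11 + 22 = 39. The row "PRGN-2009 treatment-related AE" of Grade 3 or higher shows 0 in every column.
- One-sided 95% upper bound for 0 events in n, 1 − 0.05^(1/n): for n = 39, 7.4%; for the 22 Phase 2 participants alone, 12.7%.
- Section 10.2 states that "the accrual ceiling for this protocol will be set at 50 participants", so at most 50 − 39 = 11 places remain.
- Probability of two or more events in m further participants: 1 − (1−p)^m − m·p·(1−p)^(m−1).

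| Rate p | m = 11 | m = 6 |
|---|---|---|
| 1% (assumed) | 0.5% | 0.1% |
| 2% (assumed) | 2.0% | 0.6% |
| 5% (assumed) | 10.2% | 3.3% |
| 7.4% (upper bound) | 19.3% | 6.7% |

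The column m = 6 is the allowance for inevaluable participants in section 10.2 (50 − 44). The documents give no rate for this class, so the first three rates are assumptions. The last is a bound for all vaccine-related events of Grade 3 or above, of which this class is only a part, so that row overstates the chance.

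**The case against.** The text and the logic are not in dispute. The case against acting rests on four points.

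- **Accrual may be nearly over.** Table 8 already shows 22 treated in Phase 2, equal to the planned 20 oropharyngeal plus up to 2 sinonasal participants. Further entries would mainly be replacements, so 11 is a ceiling rather than an expectation. This stands, and it lowers the impact.
- **Other safeguards exist.** The team discusses each participant about weekly (7.5.1), serious events go to the sponsor within 24 hours (8.3), Grade 3–5 events are summarised every six months (8.4), the first six Phase II participants have an interim safety assessment (10.4.7), and the study can be suspended under 13.1. The death and treatment-delay triggers also remain. A recorded Grade 4 value would probably be seen. This too stands, but none of it makes this bullet count the event.
- **The mistake may lie in the Grade 3 leg.** Since sections 3.1.1 and 3.3.1 exempt asymptomatic laboratory values at both grades, the sponsor may have meant to do so here. The documents do not settle intent. But that repair would restore the order by withdrawing protection the rule now gives at Grade 3.
- **The fix creates a mismatch with section 3.3.1.** Two Grade 4 values that need not stop either participant's vaccine would halt accrual. That mismatch already exists for persistent asymptomatic Grade 3 values, so it is not new.

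It can also be argued that a Grade 4 value that falls to Grade 3 and stays there meets the Grade 3 leg. The rule does not say so, and a value that stays at Grade 4 is exempt in any case.

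**Conclusion.** The concern holds on the plain wording. One of eight event types is ordered the wrong way: two participants with a persistent asymptomatic laboratory ADR give a count of 2, and a halt, at Grade 3, but a count of 0 under this bullet at Grade 4. Non-laboratory Grade 4 reactions and persistent symptomatic Grade 4 laboratory reactions are unaffected.

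The likely impact is small. At assumed rates of 1% to 5%, two or more such events would occur with probability 0.5% to 10.2% if all 11 remaining places were used for Phase II, and 0.1% to 3.3% with six further entries. The error affects no endpoint, sample size or analysis. The correction is still worth making, because the rule already counts the milder event and so has no reason to ignore the worse one.

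**What to change.** In the Grade 4 parenthesis of section 3.3.3, delete the words *are asymptomatic or*, so that the exemption covers only laboratory values that return to Grade 1 or lower, or to baseline, within 7 days. This moves one case, the persistent asymptomatic Grade 4 laboratory value, from not counted to counted.

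Two alternatives are less good. Changing *or* to *and* would also start counting symptomatic Grade 4 laboratory values that resolve within 7 days, so two cases change instead of one. Adding the asymptomatic exemption to Grade 3 would weaken present protection and leave persistent Grade 4 values uncounted.

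The cost is a one-phrase amendment, with no change to visits, sample size or analysis. Accrual might be halted slightly more often, but section 3.3.3 already provides for review and lifting of a halt.

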3.3.4 Dose Modification

During DLT period dose modifications are not allowed.

HPV vaccine: Vaccine doses will not be modified for an individual participant but doses may be skipped per investigator discretion. Once a dose is given to a participant that will always be the dose of vaccine they receive during this trial.

M7824: Dose reductions are not allowed but doses may be skipped per investigator discretion.

3.3.5 Toxicity Management

Table 2 Treatment Modification Guidance for Symptoms of Infusion-Related Reactions including Immediate Hypersensitivity

Infusion-Related Reactions (IRR) are an important risk for M7824.

NCI-CTCAE Grade	Treatment Modification
Grade 1 - mild Mild transient reaction; in general, infusion interruption not indicated; intervention not indicated	
 ● Increase monitoring of vital signs as medically indicated as participants are deemed medically stable by the attending Investigator. ● Hold infusion if deemed necessary by the investigator.

NCI-CTCAE Grade	Treatment Modification

Grade 2 – moderate Therapy or infusion interruption indicated but responds promptly to symptomatic treatment (for example, antihistamines, nonsteroidal anti-inflammatory drugs, narcotics, IV fluids); prophylactic medications indicated for ≤ 24 h.
	
 Stop the infusion of the study intervention. Increase monitoring of vital signs as medically indicated as participants are deemed medically stable by the attending Investigator. If symptoms resolve quickly, resume infusion at 50% of original rate with close monitoring of any worsening signs and symptoms, otherwise dosing held until resolution of symptoms with mandated premedication for the next scheduled visit. If not improving, consider administration of glucocorticoids and stop the infusion for that day. If the participant has a second IRR Grade ≥ 2 on the slower infusion rate despite premedication, the infusion should be stopped, and the investigator may consider withdrawal of this participant from the study.

Grade 3 or Grade 4 – severe or life-threatening
 
 Grade 3: Prolonged (for example, not rapidly responsive to symptomatic medication and/or brief interruption of infusion); recurrence of symptoms following initial improvement; hospitalization indicated for clinical sequelae. Grade 4: Life-threatening consequences; urgent intervention indicated. 	
 Stop the infusion of study intervention immediately and disconnect infusion tubing from the participant with additional appropriate medical measures and closely monitor until deemed medically stable by the attending Investigator. Hospitalization and/or close monitoring is recommended Administration of glucocorticoids may be required For Grade 3 or 4 IRRs, permanent discontinuation of study intervention is mandated.

NCI-CTCAE Grade	Treatment Modification
	
Once the infusion is interrupted or rate reduced to 50% of previous infusion rate, it must remain decreased for all subsequent infusions.
 
For all types and grades of infusion reactions, details about drug physical constitution, method of preparation, and infusion must be recorded.
 
Participants should be instructed to report any delayed reaction immediately.

	
Once the infusion is interrupted or rate reduced to 50% of previous infusion rate, it must remain decreased for all subsequent infusions.
 
For all types and grades of infusion reactions, details about drug physical constitution, method of preparation, and infusion must be recorded.
 
Participants should be instructed to report any delayed reaction immediately.

Table 3 Immune-related adverse events (irAEs)

Immune-related AEs are specific to immunotherapies and vary by organ system.

Following immune-related AEs are important identified risks for M7824:

- Immune-related pneumonitis
- Immune-related hepatitis
- Immune-related colitis
- Immune-related nephritis and renal dysfunction
- Immune-related endocrinopathies
- (thyroid disorders, adrenal insufficiency, type 1 diabetes mellitus, pituitary disorders)
- Immune related rash
- Other immune-related events (myositis, myocarditis, encephalitis)

Following immune-related AEs are important potential risks for M7824:

- Guillain-Barré syndrome
- Uveitis
- Pancreatitis
- Myasthenia gravis/myasthenic syndrome

Recommended guidance and management for specific irAEs are provided in the current NCCN (guideline available at <http://www.nccn.org>).

Requirements in addition to NCCN guidelines:

- Permanent treatment discontinuation is required in case of immune-related Grade 4 rash/inflammatory dermatitis, nephritis, autoimmune hemolytic anemia, hemolytic uremic syndrome, aplastic anemia, immune thrombocytopenia, acquired thrombotic

thrombocytopenic purpura inflammatory arthritis, myositis and polymyalgia-like syndrome.

- For Grade 4 immune-related lymphopenia, permanent treatment discontinuation will be required, if lymphopenia is considered immune-related in nature, no clear alternative explanation exists for the event, and it does not resolve within 14 days. Permanent treatment discontinuation is not required when the AE is manifested by a single laboratory value out of normal range without any clinical correlates. In this case, treatment should be held until the etiology is determined. If the event is not considered immune-related and resolves to Grade ≤ 1 , restarting treatment may be considered.
- For Grade 1 immune-related pneumonitis: continue treatment. If clinically indicated, monitor participants weekly or more frequently as needed with history, physical examination and pulse oximetry. If symptoms appear and/or changes in the physical exam are noted, treat as Grade 2.
- For myositis: in case of management with rituximab, treatment should be discontinued.
- For Grade 3 or 4 endocrinopathies: withhold until clinically stable or permanently discontinue depending on severity.
- For hepatitis with no tumor involvement of the liver: withhold if total bilirubin increases to more than 1.5 and up to 3 times ULN, permanently discontinue if more than 3 times ULN.
- Hepatitis with tumor involvement of the liver: permanently discontinue if total bilirubin increases to more than 3 times ULN.

Table 4 Management of M7824 mediated Skin Reactions

Skin reactions are considered important identified risk for M7824.
 
 • Hyperkeratosis • Keratoacanthoma • Cutaneous squamous cell carcinoma (cSCC) • Basal cell carcinoma • Actinic keratosis 
Management
 
 • Discontinuation or termination not required in most cases. Continuation of treatment should be evaluated by the Investigator. • Emollients may be used • Develop diagnostic and treatment plan in collaboration with Investigator and dermatologist • Treatment follow-up will depend on number and localization of lesions. 
 ○ Single lesion: full excision may be recommended
--


 ○ Multiple lesion or location not suitable for full excision: Mohrs surgery, cryotherapy or other standard treatment options depending on pathology. Retinoids may be used after discussion with Investigator. ● Close clinical follow-up for re-evaluation, resolution and potential recurrence should be implemented ● In general, treatment of skin lesions should be based on local guidelines/standard of care.

Additional consideration: Keratoacanthoma lesions may resolve spontaneously without surgical intervention within weeks after discontinuing M7824.
 
Consult with Medical Monitor as needed for management of skin lesions.

Table 5 Management of Anemia

 ● Anemia is considered an important identified risk for M7824. ● All relevant hematological testing for treatment-related anemias should be done prior to a blood transfusion, if clinically feasible
Basic Anemia Evaluation

 ● CBC with emphasis on red cell indices ● If indicated and at clinical discretion, the following should be considered: 
 ○ Iron studies ○ Serum Folate and Vit B12 values ○ Coagulation factors ○ Fecal occult blood ○ Urinalysis ○ Hormone panel: TSH, Erythropoietin ○ Peripheral blood smear
Further Recommendation Based on Suspected Etiology (in Addition to Basic Anemia Testing)

 ● Suspected Hemolysis 
 ○ bilirubin, LDH, Coombs test, haptoglobin ● Suspected bleeding: 
 ○ Consider imaging/interventional radiology consultation as indicated ○ Consider imaging and/or endoscopy as clinically indicated ● Suspected aplastic anemia: 
 ○ Hematology consultation ○ Consider bone marrow aspiration/morphologic evaluation

Additional consideration:

In general, blood transfusions and erythroid growth factors are permitted as clinically indicated.

Table 6 Management of Bleeding Adverse Events

Bleeding Adverse Events	

 • Bleeding adverse events are considered important identified risk for M7824. • In general, mild and moderate mucosal bleedings resolve without discontinuation of treatment. • These events may include, but are not limited to the following: 
 ◦ Epistaxis ◦ Hemoptysis ◦ Gingival bleeding ◦ Hematuria 	
Non-tumor Bleeding	
Grading	Management
Grade 2	
 • If resolves to Grade ≤ 1 by the day before the next infusion, study intervention may be continued • If not resolved to Grade ≤ 1 by the day before the next infusion, but is manageable and /or not clinically relevant, assessment if clinically reasonable to administer the following infusion will be per PI discretion.
Grade 3	
 • Permanently discontinue treatment unless an alternative explanation can be identified (such as concomitant use of antithrombotic agents, traumatic events, etc.) • In case of alternative explanations, hold study treatment until the event recovers to Grade ≤ 1
Grade 4	
 • Treatment must be permanently discontinued if no alternative explanation is identified.
Tumor Bleeding	
Grade ≥ 2	
 • Study treatment must be held till the event recovers to Grade ≤ 1

	
• Permanently discontinue treatment if the Investigator considers the participant to be at risk for additional severe bleeding.
--	---

Table 7 Impaired Wound Healing

• Impaired wound healing is considered important potential risk for M7824• Elective surgery on study will be allowed per PI discretion• It is recommended to hold study intervention for approximately 4 weeks post major surgery for observation.	
--	--

Post-operative wound healing should be closely monitored

Abbreviated Title: Combo Immunotx in HPV OPSCC

Version Date: 09.20.2023

